In addition to settings listed above, the following parameters are to be tested in this study. 3 Intensity (I) settings (6, 12, and 24 W/cm²), 6 duty cycle (DC) settings ranging from 1-70%, 3 duration (Dur) settings ranging from 100ms-1s, and 4 pulse repetition frequency (PRF) settings ranging from 10-1000Hz. As this is a parametric design, we are testing 216 ultrasound settings. Though each setting will take less than 1 minute to test, testing is

expected to be divided between 6 study sessions (up to 36 per session) to reduce burden to the participant.

These levels of energy are adhered to in human ultrasonic neuromodulation studies though there are no specific guidelines for energy deposition for ultrasonic neuromodulation and indeed, explicit expository and dosimetry for diagnostic and therapeutic applications, despite their prevalence and long history, has proven challenging and is still largely lacking. Ultrasound for transient neuromodulation is different from the use of ultrasound for surgery where very high intensities are used to thermally ablate tissues or for blood-brain barrier (BBB) opening where high intensities are also used in combination with contrast agents to intentionally produce cavitation as a means of opening the BBB. To date, a total of $N = 179$ in 8 published studies of healthy neurologically intact participants (plus one 1 TBI patient) have undergone a variant of LIFU for neuromodulation with no published report of severe adverse events. We have published on minor adverse events from LIFU ([name] et al. 2020).

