8.0 Procedures Involved

- 8.1 *Describe and explain the study design:*

This is a systematic study of set parameters in a multiple visit study.

Session 1: MRI and CT anatomical scans

Session 2-7: LIFU parameter testing with TMS and EMG while utilizing neuronavigation and physiological data collection such as PPG, BP, ECG, Respiration, and/or GSR.

- 8.2 *Provide a description of:*

- *All research procedures being performed*
- *If the study has more than one procedure, session, and/or subject population, describe each procedure, session, and/or study population separately. For complex studies, you are encouraged to include a figure or chart.*

Recruitment and Screening: Individuals indicating interest in participating in this research study will complete a screening and demographic form as part of the screening process (see Safety Screening Form and Demographic Form). This information will be reviewed to determine eligibility and to screen for any contraindications to MRI, CT, and TMS.

Consent: Participants will be asked to sign a consent form upon arrival for their first study visit. Participants will have as much time as they need to review the consent form and may ask questions of the PI or study team prior to participation.

Pregnancy Screening: Prior to any study procedures, female participants will provide a urine sample which will be screened for pregnancy. As indicated in the consent form, if

testing indicates the participant is pregnant, they will be notified and excluded from the study.

Participants will be healthy adults age 18-65 with no contraindications to MRI, CT, or TMS. We will enroll approximately 80 individuals.

This study includes low-intensity focused ultrasound (LIFU), transcranial magnetic stimulation (TMS), magnetic resonance imaging (MRI), and computed tomography (CT). Additionally, stereotaxic neuronavigation is utilized.

Study Procedures:

Session 1	Session 2-7
Imaging	36 Parameter Trials
MRI & CT	LIFU + TMS
2.5 hours	2.5 hours

*parameters per session will be chosen randomly within the set values

Session 1 - An MRI and CT exam will be performed and questionnaires will be administered.

Sessions 2-7 - Utilizing imaging collected on previous visit, subjects will complete a testing session. These sessions will involve LIFU and TMS stimulation. Additionally EMG, PPG, BP, ECG, Respiration, and GSR will be collected. Questionnaires will be administered at each session.

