LIFU: Low-intensity focused ultrasound (LIFU) is a method of brain neuromodulation using ultrasonic acoustic energy. An ultrasound transducer is placed on the participant's head and is tracked using the neuronavigation system. Brief ultrasound pulses are delivered to the desired brain area. A small amount of ultrasound gel will be placed on the face of the single-element focused ultrasound transducer. The transducer will then be fitted on the scalp over the desired brain area and held in place with a mechanical arm. Brief pulses (0.1-1.0 seconds; duty cycle 1 – 70%; pulse repetition frequency 10 – 1000 Hz) of low-intensity (< 50 W/cm² Isppa), sub-thermal ultrasound (0.3 - 0.5 MHz) will be delivered in order to determine the area of activation, as well as the patterns of brain activity generated. Subjects may experience a mild buzzing sensation on their scalp depending upon stimulation parameters used. Participants will be familiarized with the sensations before formal testing. The ultrasound intensity used will be below the intensities recommended for the safe use of ultrasound by the FDA (190 W/cm² Isppa) and will be brief in duration at these low-intensities as not to generate any heating. While no discomfort is anticipated, participants will be informed if they experience any warming sensation on their scalp or discomfort to notify the investigator and the procedure will be immediately terminated. Participants may be given ear plugs to wear during the procedure and/or a white noise machine may be utilized in the testing space. This is to provide ear protection and noise cancellation to reduce participant focus on LIFU device function. We have significant experience using LIFU including our published reports of human neuromodulation experiments.

TMS: transcranial magnetic stimulation (TMS) is a noninvasive method of stimulating the brain using magnetically induced electrical currents. The stimulating coil is placed over a subject's motor cortex and a single pulse is conducted. This is repeated 10-20 times at an inter-stimulus interval of 5-10 seconds per trial. A threshold setting will be determined for each participant before each study session to obtain an average motor evoked potential of approximately 0.75mV, measured with EMG recordings. This will be the setting used throughout the testing session.

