EMG: Electromyography (EMG) involves attaching disposable surface electrodes to the skin overlying muscles of interest of the hand and forearm in order to record muscular activity. Identification of the muscle is achieved by asking the participant to hold a light tonic contraction. The skin may be prepared with a mild abrasive gel to remove dead skin and surface debris and subsequently disinfected with rubbing alcohol. EMG electrodes are held in place with double sided tape. This signal is used to detect LIFU effects and TMS amplitude.

PPG, GSR, ECG, BP, Respiration: Photoplethysmograph (PPG) and galvanic skin response (GSR) will be collected using a lightweight wearable Shimmer3 GSR+ unit and blood pressure will be collected using a wireless blood pressure monitor (QardioArm). A commercial respiration belt (SleepSense) will be wrapped around the chest to collect continuous respiration data. Electrocardiogram (ECG) will be collected using two leads. This data is collected to assess for any effects of ultrasound but more importantly as a monitor of the state of the participants' autonomic nervous system as a potential contributor/confound that may affect responses.

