Questionnaires: Questionnaires will be collected either electronically using a VT approved platform such as Redcap, or on paper. The following questionnaires will generally be completed during the imaging and consent visit but may be completed at following visits if time does not allow during the first visit: Beck Depression Inventory-II (BDI), Beck Anxiety Inventory (BAI), State Trait Anxiety Inventory (STAI), International Physical Activity Questionnaire (IPAQ), Medical Outcomes Survey Short Form-8 (SF-8), Sleep Scale from the Medical Outcomes Study, Patient Health Questionnaire-2 (PHQ-2), Generalized Anxiety Disorder 2-item (GAD-2), Tobacco, Alcohol, Prescription medications, and other Substance Tool (TAPS), and Perceived Stress Scale (PSS). Questionnaires may be used as a means of documenting potential confounds such as anxiety, fear, depression, etc. Questionnaires are estimated to take 30-45 minutes to complete. Additionally, the STAI (state only), Experience Questionnaire, Daily Questionnaire, and Report of Symptoms questionnaires will be administered at all stimulation sessions (sessions 2-7). The Daily Questionnaire exists to help quantify any variance between participant sessions. This includes items such as amount of sleep, hormone changes, and caffeine intake. Lastly, subjects will be contacted up to one month following the final session to complete the participant Report of Symptoms questionnaire. All questionnaires are attached to this application.

8.3 *Describe:*

- *Procedures or safeguards intended to reduce the probability and magnitude of risks. (For example: Reducing the risk of injury in a virtual reality study either by having the subjects sit during the study or by providing an obstacle-free space for walking.)*
- *Be sure to describe all drugs and devices used in the research, when they will be administered or used, and their purpose.*
- *Methods used to collect data about subjects. Please upload all data collection forms to Protocol Management. Some common examples are:*
 - *Screening questionnaires*
 - *Survey(s), including online surveys*
 - *Demographic questionnaire(s)*
 - *Interview guide(s), e.g., questions or pool of questions for semi-structured interviews*
 - *Focus group guide(s)*
 - *Other documents used to collect data*

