Investigation of Low-intensity Focused Ultrasound Parameters

NCT: NCT05134233

09/12/2024

Statistical Analysis Plan (SAP) for ClinicalTrials.gov Submission

Study Title: Investigating Neuromodulatory Effects of Low-Intensity Focused Ultrasound (LIFU) in Humans

1. Objective:

This study aims to assess the effects of varying parameters of low-intensity focused ultrasound (LIFU)—such as intensity, duration, duty cycle, and pulsing—on neuromodulation in the human brain. The primary focus is on evaluating changes in motor-evoked potential (MEP) amplitude when LIFU is applied concurrently with transcranial magnetic stimulation (TMS).

2. Study Design:

2.1 Interventions:

The study involves the application of LIFU using the following 20 parameter combinations:

- **Intensity levels:** 6 W/cm² and 24 W/cm²
- **Duty cycles:** 1%, 10%, 30%, 50%, and 70%
- **Durations:** 100 ms and 500 ms
- **Pulsing conditions:** Pulsed versus continuous delivery evaluated in 4 combinations

2.2 Study Type:

This is a fully parameterized, repeated measures design in which LIFU is delivered concurrently with TMS. Each subject experiences all combinations of LIFU parameters.

2.3 Data Collection:

- **MEP amplitude:** Measured as the peak-to-peak response for each LIFU parameter combination, with 20 stimulations per trial per subject.
- **Normalized MEP values:** Calculated by normalizing MEP amplitudes for each parameter combination to baseline (pre-LIFU) values.

3. Outcome Measures:

3.1 Primary Outcome Measure:

- **MEP Amplitude:** Normalized MEP amplitude, analyzed across the 20 parameter combinations of LIFU.

3.2 Secondary Outcome Measure:

- **Pulsed vs. Continuous Ultrasound:** Effects of pulsing on MEP amplitude will be evaluated.

4. Statistical Analysis Plan:

4.1 Power Analysis:

Based on preliminary data from a pilot study (N=5), we observed maximal changes in MEP amplitude of:

- **Excitatory effects:** 46.35% \pm 12.33%
- **Inhibitory effects:** -25.54% \pm 15.56%

- **Minimal effects:** $5.99\% \pm 7.87\%$ with less optimal parameter combinations.

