To detect a meaningful change in MEP amplitude, we calculated a required sample size of **N=56 participants**. This is sufficient to detect a **15% change** in MEP amplitude (minimum clinically significant change) with a power of **0.8** and a significance level of **p = 0.05**. This sample size may not detect minimal changes (~6%), but is adequate to capture meaningful excitatory and inhibitory effects across parameter combinations.

4.2 Assumptions Testing:

- **Normality of MEP Amplitudes:** Tested using **Bartlett's test for sphericity** ($p < 0.05$). If assumptions of normality or homogeneity of variances are violated, non-parametric tests will be used.

4.3 Primary Analysis:

- **Paired t-tests:** We will compare baseline normalized MEP values with post-intervention MEP values for each LIFU parameter combination. To control for multiple comparisons, a **Bonferroni correction** will be applied, adjusting the significance level to **p < 0.0025** ($0.05/20$).
- **Three-Way Repeated Measures ANOVA:** A 3-way repeated measures ANOVA will be performed to assess the main effects and interactions between the following factors:
 - **Intensity:** 6 W/cm² vs. 24 W/cm²
 - **Duty Cycle:** 1%, 10%, 30%, 50%, 70%
 - **Duration:** 100 ms vs. 500 ms
- **Post-hoc testing:** If significant main effects or interactions are observed, **Tukey's Honest Significant Difference (HSD) test** will be applied for pairwise comparisons. Tukey's HSD will control the family-wise error rate, ensuring reliable comparisons between parameter combinations.

4.4 Pulsed vs. Continuous Analysis:

A separate **three-way repeated measures ANOVA** will be conducted to evaluate differences between pulsed and continuous LIFU delivery. The main factors assessed will be:

- **Intensity:** 6 W/cm² vs. 24 W/cm²
- **Number of Cycles:** 35,000 vs. 75,000
- **Pulsing Condition:** Pulsed vs. Continuous

Post-hoc analyses using **Tukey's HSD** will follow if significant results are observed.

5. Handling Missing Data:

If missing data arises, participants with missing measurements for key outcomes will be excluded from specific analyses. However, where possible, **multiple imputation** methods will be used to handle missing data. Sensitivity analyses will be conducted to assess the robustness of the results in the presence of missing data.

6. Assumptions and Corrections:

6.1 Assumptions for Parametric Testing:

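### Settings are allocated at random to six stimulation sessions, but no planned analysis includes session, so setting contrasts lose precision (not validity) if the settings really are split

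*Protocol*

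**What the plan says.** **Allocation.** Protocol 7.3 describes 216 settings divided over six sessions, at most 36 in each. The note under the table in Protocol 8.2 says "parameters per session will be chosen randomly within the set values".

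**What is set per session.** The TMS entry in Protocol 8.2 says "A threshold setting will be determined for each participant before each study session to obtain an average motor evoked potential of approximately 0.75mV", and that setting is then kept for the whole session.

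**Session-state data.** The Questionnaires entry in Protocol 8.2 says "The Daily Questionnaire exists to help quantify any variance between participant sessions"; its items include sleep, hormone changes and caffeine. The physiological recordings monitor autonomic state as "a potential contributor/confound that may affect responses".

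**Analysis.** Protocol 5.2 plans four-way ANOVAs on intensity, duty cycle, duration and PRF. SAP 4.3 plans paired t-tests and says "A 3-way repeated measures ANOVA will be performed to assess the main effects and interactions" of intensity, duty cycle and duration. SAP 4.4 adds a second three-way ANOVA for pulsing. None has a term for session, or a covariate.

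**SAP design.** SAP 2.1 says "The study involves the application of LIFU using the following 20 parameter combinations" and SAP 2.2 adds "Each subject experiences all combinations of LIFU parameters". The SAP does not say how these are spread over sessions. SAP 2.3 normalises to a pre-LIFU baseline without giving the number or timing of baselines.

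**The concern.** Under the Protocol, session is the block to which settings are allocated, and each block has its own stimulator setting. Two settings tested in different sessions therefore differ by their own effects plus whatever changed between those days. An analysis that ignores the block leaves that day-to-day difference in the error term, while one that models it can remove most of it from comparisons made within a session.

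At stake is the precision of the main effects, interactions and pairwise comparisons between settings, which is what the study is for. The Protocol itself names between-session variation as something to quantify, but no analysis takes it up.

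**Working it through.** **1. The plan's own counts.** Protocol: 3 × 6 × 3 × 4 = 216 settings, and 216 / 6 = 36 per session. SAP: 2 × 5 × 2 = 20 combinations. All reproduce. Twenty is below 36, and so is 20 + 4 = 24 if the four pulsing combinations are additional. The SAP's settings could therefore fit in one session.

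**2. Inputs and assumptions.** N = 56 completers (Protocol 14.1, SAP 4.1). Within-participant variance is scaled to 1, with share ρ due to session and 1 − ρ residual. No document gives ρ, so 0.1 to 0.5 is an assumed range. Allocation is taken to be drawn separately for each participant.

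**3. Formulas.** There are *v* settings, with *k* in a given session; sums run over sessions. Per-participant variance of the difference between two settings:

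- Without session: 2(1 − ρq), where q = Σk(k − 1) / [v(v − 1)] is the chance that two settings share a session.
- With a random session effect: 2 / I, where I = (T − A/B) / (v − 1). With d = 1 − ρ + kρ: T = Σ[k/(1 − ρ)](1 − ρ/d), A = Σk/d², B = Σk/d.

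Both variances are divided by N, which cancels in the ratio.

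**4. Worked case: 20 settings over six sessions (4, 4, 3, 3, 3, 3), ρ = 0.5.**

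- q = (2 × 12 + 4 × 6) / (20 × 19) = 48/380 = 0.126. Without session: 2(1 − 0.063) = 1.874.
- d = 2.5 for k = 4 and 2.0 for k = 3. T = 16 × 0.8 + 24 × 0.75 = 30.8. A = 8/6.25 + 12/4 = 4.28. B = 8/2.5 + 12/2 = 9.2.
- I = (30.8 − 0.465)/19 = 1.597. With session: 2/1.597 = 1.253.
- Variance ratio 1.874/1.253 = 1.50. SE reduction 1 − √(1.253/1.874) = 18%.

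A generalised least squares calculation over 56 randomly drawn allocations gives 1.49, which agrees.

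**5. Results over the range** (variance without session / with random session, and SE reduction):

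| Layout | ρ = 0.1 | ρ = 0.3 | ρ = 0.5 |
|---|---|---|---|
| 216 settings, 6 sessions | 1.07, 3% | 1.33, 13% | 1.80, 25% |
| 20 settings, 6 sessions | 1.02, 1% | 1.16, 7% | 1.49, 18% |
| 20 settings, 2 sessions | 1.03, 1% | 1.17, 8% | 1.45, 17% |
| 20 settings, 1 session | 1.00, 0% | 1.00, 0% | 1.00, 0% |

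For scale, at ρ = 0.5 with 20 settings over six sessions, about 56/1.49 = 38 participants with session modelled match 56 without it.

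**6. Random or fixed session.** With session fixed, the variance is 2(1 − ρ)(v − 1)/(v − b) for b sessions. For 20 settings over six sessions at ρ = 0.1 this is 2 × 0.9 × 19/14 = 2.44, against 2(1 − 0.0126) = 1.97 with no session term at all. A fixed effect thus loses precision there, and breaks even only near ρ = 0.3.

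**7. What session-state covariates add.** A measure taken once per session can explain only session variance. If it explains 20% of that at ρ = 0.5 (20 settings, six sessions), session variance falls from 0.50 to 0.40. Recomputing I with 0.40 as the session variance and 0.50 as the residual gives a contrast variance of 1.236 against 1.253, a further SE reduction of 1 − √(1.236/1.253) = 0.7%. Over ρ = 0.1 to 0.5, the further gain stays below 1% when covariates explain 5% to 20% of session variance.

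**The case against.** The strongest reply is that the point joins two designs. The six-session split belongs to the Protocol's 216 settings, while the SAP's model covers 20 combinations that could be run in one session, where nothing is lost. This stands as a condition on the size of the gain. It does not dispose of the point: neither document describes a single-session layout, and even two sessions give most of the loss seen with six when ρ is large.

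A second reply is that resetting TMS each session and normalising to baseline already remove part of the session level. That is fair, and it argues for a smaller ρ. How much is removed cannot be judged until the baseline's timing is stated.

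Three stronger readings are tempting and are not supported:

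- A reader might infer that each session has a single baseline, whose error is then shared by all settings in that session. Only the TMS setting is stated to be per session; the baseline could equally be taken per block or per setting.
- A reader might apply 1 − √(1 − R²) to all remaining variance and expect covariates with R² of 5% to 20% to cut the SE by a further 3% to 11%. Once-per-session measures cannot reach the residual within sessions, so that figure does not apply.
- A reader might infer that the state measures are ready-made baseline covariates. The Protocol says they are collected at the stimulation sessions, not that they precede the first setting. It says questionnaires may document confounds, and does not commit to adjusting for them.

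**Conclusion.** The point holds as a conditional loss of precision. Session is a block in the Protocol's allocation and is absent from every planned analysis. Modelling it as random would lower the SE of setting contrasts by about 1% to 18% (20 settings over six sessions) or 3% to 25% (216 settings), for an assumed session share of 0.1 to 0.5. The gain is zero if all 20 settings run in one session, and negligible if the share is small.

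These figures rest on an assumed share, on variance components treated as known, and on allocation drawn separately for each participant. They concern comparisons between settings, not the paired t-tests against baseline in SAP 4.3. A reader might infer that omitting session biases the results; with random allocation it does not. The change is worth making because it costs little and matches the analysis to the allocation. Its absence does not invalidate the planned tests.

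**What to change.** 1. Reconcile the Protocol and SAP on how many settings are tested, over how many sessions, and how they are allocated to sessions within each participant.
2. State in the SAP when the pre-LIFU baseline is taken (per session, per block or per setting) and from how many pulses.
3. Replace the repeated measures ANOVAs with a mixed model of log MEP: the same factors and interactions as fixed effects, with random participant and random session-within-participant effects. Keep session random, since a fixed effect with three or four settings per session can cost precision.
4. State the role of the Daily Questionnaire, state anxiety and physiological measures as secondary or descriptive. Use them for adjustment only if taken before the first setting of the session, and expect little further precision from them.

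**Cost.** SAP wording, slightly more analysis work and one extra variance component. With a small session share the random effect does almost no harm (variance ratio 1.005 at a share of 0.05 for 20 settings over six sessions). If the state measures are not now taken before stimulation, using them for adjustment would also need a change in procedure.

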9.0 Data and Specimen Long Term Storage and Use

9.1 *If you will store data or specimens for future use, describe where you will store the data or specimens, how long they will be stored, and how and by whom the data or specimens will be accessed:*

All data collected from subjects will be assigned a coded designation. MRI, CT, EMG, and behavioral data will be stored on secure FBRI servers indefinitely. All of this data will have no identifying information. Only the code will link it to the PII of the subject. The de-identified data will be made available to authorized study staff, and may be stored elsewhere such as Dropbox, iCloud, or a local drive on a desktop or laptop. Further, after publication of results, de-identified data may be made available to the public in accordance with funding and publication requirements, or otherwise.

9.2 *For specimens, list the data to be stored or associated with each specimen:*

N/A

9.3 *Describe the procedures to release data or specimens outside of the research team, including the process to request a release, approvals required for release, who can obtain data or specimens, and what data will be provided with specimens:*

Prior to publication of results, de-identified data will be made available to study staff as listed on the approved IRB. After publication, de-identified data may be made public as required by funding sources, journals, or otherwise.

9.4 *Describe the identifiers to be included with stored data or specimens, as well as any key or code that could be used to make them identifiable. Describe where the code will be stored, who will have access to it, and when it will be destroyed:*

Data will be coded using a randomly generated identifier. The study key linking name to identifier is stored digitally under password access, only accessible by authorized members of the research team.

Participant Social Security Number (or Taxpayer ID) and street address are collected in order to compensate participants, via W9 form or W-8BEN. This information is entered into the ClinCard system, which is a HIPAA compliant payment system approved by Virginia Tech. After entry the form is stored by central administration at Virginia Tech to be used if it is required. Study staff do not store documents with SSN or address long term. International participants will also be asked to provide a copy of passport, visa documents, any work authorizations, as well as the Foreign National Data Form.

Documents with other identifiers, such as name, phone number, email, or elements of dates are stored separately from de-identified study data, either via encryption or in a locked file cabinet, accessible only by study staff.

9.5 *Please select the identifiers you will obtain (whether directly from participants or from another source), including but not limited to:*

	Name
	Geographical subdivisions smaller than a state, including street address, city, county, precinct, zip code, and equivalent geocodes (note, the initial three digits of a zip code are not considered identifiable)
	Elements of dates (except year) for dates directly related to an individual, including birth date, admission date, discharge date, date of death, and single year of age over 89 and all elements of dates (including year) indicative of such age (note, such ages and elements may be aggregated into a single category of age 90+)

	Phone numbers
	Fax numbers
	Electronic mail addresses (e-mail)
	Social Security numbers
	Medical record numbers
	Health plan beneficiary numbers
	Account numbers
	Certificate/license numbers
	Vehicle identifiers and serial numbers, including license plate numbers
	Device identifiers and serial numbers
	Web Universal Resource Locators (URLs)
	Internet protocol (IP) address numbers
	Biometric identifiers, including finger and voice prints (audio recording)
	Full face photographic images and any comparable images (including video recording)
	Student record number or identification number
	User name for online or computer accounts
	Any other unique identifying number, characteristic, or code (note this does not mean the unique code assigned by the investigator to code the data): Passport ID

